2.2.2 Derivation rules

- Time to first weaning (hours) = date/time of first dose reduction – date/time of first study drug administration
Note: missing data will not be imputed.
- Number of rescue doses administered = sum of rescue dose administrations (SUPPEC.QVAL = ‘Y’ when SUPPEC.QNAM is ‘RESCUEDO’)
Note: 0 for subjects not requiring rescue doses.

2.2.3 Inferential statistics

No inferential statistics will be performed.

2.2.4 Presentation of results

All data relevant to the following primary and secondary efficacy endpoints will be listed:

- Duration of treatment
- Time to first weaning
- Requirement for adjunctive drug therapy
- Number of rescue doses
- Relapse of NOWS

2.3 PHARMACOKINETICS

2.3.1 *Available data*

Blood samples will be collected for the determination of CHF6563 at the time points indicated in the schedule of assessments (see section 9.1).

2.3.2 *Presentation of results*

Individual CHF6563 blood concentrations and actual blood sampling times from drug administration for PK assessments will be listed.

3. SAFETY ANALYSES

3.1 ADVERSE EVENTS

3.1.1 *Available data*

Adverse events (AEs) are coded into system organ classes and preferred terms using the medical dictionary for regulatory activities (MedDRA). For each AE, start and stop date(time)s are collected as well as severity, a seriousness flag, treatment-relatedness, action taken towards the study drug and outcome.

3.1.2 *Derivation rules*

Pre-treatment AEs are defined as AEs starting between date(time) of informed consent and the date(time) of first study drug administration – 1 minute.

Treatment-emergent adverse events (TEAE) are defined as AEs starting on or after first administration of any study drug.

Peri-dosing TEAEs are defined as AEs included in the list below occurring during or shortly after study drug administration, i.e. within 10 minutes from the start of study drug administration:

- mouth irritation or inflammation,
- apnea, desaturation,
- brady/tachycardia,
- cough,
- immediate swallowing of sublingual drug,
- regurgitation,
- vomiting occurring after administration.

Note: the list of preferred terms to be selected as peri-dosing TEAEs will be finalized prior to database lock and documented in the DRR. For AEs start dates with missing time information where no other database information indicates that AE started outside the peri-dosing interval, the worst-case principle will be applied and these AEs will be considered as peri-dosing.

Post-treatment AEs are defined as AEs starting on or after the start of the follow-up phase.

Based on their start date(time), AEs will be allocated to the phase during which they started. Phases are defined in section 5.2.1. In case the AE start date(time) is incomplete or missing and the AE could consequently be allocated to more than one phase, a worst-case allocation will be done as detailed below:

- Treatment phase vs. non-treatment phase: AE will be allocated to the treatment phase unless the available parts of the AE stop date(time) provide evidence for allocating to the non-treatment phase.

A fatal AE is defined as an AE with outcome 'fatal'.

An AE for which the study drug was discontinued is defined as an AE with action taken 'drug withdrawn'.

AE onset and duration will be calculated as follows when start and stop dates are fully known:

- AE onset day (vs. first administration) =
 - AE start date < date of first administration: AE start date – date of first administration
 - AE start date \geq date of first administration: AE start date – date of first administration + 1 day
- AE duration (rounded as detailed in section 5.3.3) =
 - In minutes: AE end date/time – AE start date/time + 1 minute
 - In hours: AE end date/time – AE start date/time + 1 hour
 - In days:
 - AE end date – AE start date + 1 day
 - study discontinuation date – AE start date + 1 day (when the AE start date is fully known but the AE is not resolved at the end of the study)

In this case the duration will be presented as “>x days”.

Note: If AE duration is less than 1 hour, the duration will be presented in minutes. If the AE duration is 1 hour or more, but less than 1 day, it will be presented in hours. If AE duration is 1 day or more, it will be presented in days.

[figure not shown]

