- Treatment administration: treatment doses will be calculated according to birth weight (which should be rounded to the second decimal place) and the NOWS score which will be assessed and recorded every 4 hours.
- Feeding status: breastfeeding, formula feeding, mixed feeding, and the proportion of maternal breastmilk intake during this period of time i.e. randomization to stabilization will be recorded.
- Liver function test (AST, ALT): will be performed after first dose and following treatment stabilization prior to the first weaning dose and recorded.
- Blood sampling for CHF6563 pharmacokinetics will be performed.
- Further concomitant medications/procedures and adverse events as well as changes in those already reported will be recorded.

Clinical Study Code No.: CLI-06563AA1-02	Version No.: 6.0
IND No.: 131,339	Date: 18 March 2021

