12.3.7 Safety variables

Adverse Events

Safety analysis will be based on Safety population. All adverse events starting on or after the time of first study drug intake will be classified as treatment emergent adverse event (TEAE). Any adverse events started after the informed consent signature and before the time of first study drug intake will be classified as pre-treatment adverse events.

The number of babies who experienced at least one TEAE, drug-related TEAE, serious TEAE, serious related TEAE, TEAE leading to study discontinuation, TEAE leading to death, and peri-dosing TEAEs will be summarized by treatment arm. Summaries will be presented overall (number and percentage of babies having at least one event, total number of events) and by system organ class and preferred term (number and percentage of babies having at least one occurrence of that event).

All adverse events will be listed.

Pre-treatment adverse event will be listed only.

The peri-dosing AEs are defined as adverse events occurring during or shortly after administration of study treatment, i.e. within 10 minutes from the start of study drug administration.

Vital signs

Vital signs will be summarized at each planned time point by means of descriptive statistics. At each timepoint when vital signs are collected, mean, min, max and standard deviation of the observed values and change from baseline will be presented, in addition to being listed.

Laboratory data

Sites will use local labs to obtain liver enzymes analysis-function testing. When consistent with site clinical practice, sites will use local labs to collect hematology and blood chemistry. The laboratory values and the change from baseline for continuous laboratory parameters will be summarized by descriptive statistics at each planned time point. All laboratory data will be listed with abnormal values flagged.

Head circumference (and percentile) and body weight (and percentile)

Head circumference (and percentile) and body weight (and percentile) and their corresponding changes from baseline will be summarized using descriptive statistics at each planned time point.

Additional Safety Variables

The following parameters collected only at the end of the treatment period will be listed only:

- Neurological and behavioral assessment

Analysis of safety variables collected at the 18-month follow up visit will be described in the SAP.

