3.1.3 Presentation of results

Tables will present TEAEs and post-treatment AEs only. Pre-treatment AEs will only be listed.

An overview table will show the number and percentage of subjects with at least one event and the number of events by treatment for the following:

- TEAEs
- Serious TEAEs
- Non-serious TEAEs
- ADRs
- Serious ADRs
- Severe TEAEs
- TEAEs leading to study drug discontinuation
- TEAEs leading to death
- Peri-dosing TEAEs
- ADRs leading to study drug discontinuation
- ADRs leading to death
- Peri-dosing ADRs
- Post-treatment AEs

All AEs, including pre-treatment events and all coding information will be listed. AEs started after date of last study medication intake will be flagged. Blank system organ classes and preferred terms, if any will be shown as ‘Not Available’.

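### Treatment-emergent status depends on start time alone, so an adverse event open at first dose that worsens on study drug can be left out of the only adverse event table

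*SAP*

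**What the plan says.** **Definition.** SAP 3.1.2: "Treatment-emergent adverse events (TEAE) are defined as AEs starting on or after first administration of any study drug". Protocol 12.3.7 agrees: "All adverse events starting on or after the time of first study drug intake will be classified as treatment emergent adverse event (TEAE").

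**Pre-treatment class.** SAP 3.1.2: "Pre-treatment AEs are defined as AEs starting between date(time) of informed consent and the date(time) of first study drug administration", less one minute. What happens to the event after the first dose plays no part.

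**Phase.** SAP 3.1.2: "Based on their start date(time), AEs will be allocated to the phase during which they started". The one exception is for an incomplete or missing start: "AE will be allocated to the treatment phase unless the available parts of the AE stop date(time) provide evidence for allocating to the non-treatment phase".

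**Output.** SAP 3.1.3: "Tables will present TEAEs and post-treatment AEs only. Pre-treatment AEs will only be listed". Protocol 12.3.7 also says: "Pre-treatment adverse event will be listed only". SAP 8.1 has a single adverse event table, 14.3.1.1. In SAP 8.2, Listings 16.2.7.3 to 16.2.7.9 (serious, non-serious, ADR, serious ADR, severe, discontinuation, death) are all built as subsets of the treatment-emergent Listing 16.2.7.2.

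**Recording.** At treatment-period visits (Protocol 7.1.3 and 7.1.4), further "adverse events as well as changes in those already reported will be recorded". Protocol 10.8 asks that important changes seen at later visits be reported as adverse events. The fields named in SAP 3.1.2 are start, stop, severity, seriousness, relatedness, action taken and outcome. A date of worsening is not among them.

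**The concern.** Adverse events are collected from consent, or from birth if consent came earlier, and treatment may begin up to 7 days after delivery. A baby can therefore receive the first dose with an event already open. If that event gets worse on an opioid, it is an on-treatment harm in substance, but the start-time rule calls it pre-treatment.

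Safety and tolerability is a primary objective, and Table 14.3.1.1 is the one table of safety outcomes that SAP v2.0 keeps. Its severity, seriousness, discontinuation and death rows are restricted to treatment-emergent events or ADRs. A row could read zero when a dosed baby had such an outcome, and a reader of the table would have no sign of it.

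**Working it through.** No figure in the plan is in dispute, so the check is to apply the rules as written.

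**Step 1. Test cases.** Take an event with a complete start time before the first dose, in a dosed baby, where the site has not opened a new record for the change.

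| What happens after first dose | Class | Missing from | Still shown in |
|---|---|---|---|
| Intensity rises to severe | Pre-treatment | Severe row of 14.3.1.1; Listing 16.2.7.7 | Listing 16.2.7.1 |
| Becomes serious | Pre-treatment | Serious row; Listing 16.2.7.3 | Listing 16.2.7.1 |
| Outcome fatal | Pre-treatment, though it meets the SAP's own definition of a fatal event | Death row; Listing 16.2.7.9 | Listing 16.2.7.1; also 16.2.1.3 if it ended participation |
| Study drug withdrawn | Pre-treatment, though it meets the SAP's own definition of a discontinuation event | Discontinuation row; Listing 16.2.7.8 | Listing 16.2.7.1; also 16.2.1.3 if it ended participation |

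**Step 2. Contrast with an incomplete start.** Give the same event an incomplete or missing start that could fall in either phase. It goes to the treatment phase unless the stop date shows otherwise, so it would normally be counted. A fully dated event known to have worsened on drug is thus handled less conservatively than a poorly dated one.

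**Step 3. The ADR rows.** Protocol 10.1 defines an ADR by causality, with no start-time condition. The restriction comes from the general sentence in SAP 3.1.3 and from Listing 16.2.7.5 being a subset of the treatment-emergent listing. It is less explicit than for the other rows, but it leads to the same omission.

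**Step 4. Size of one omitted baby.** SAP 6.1 gives 7 babies randomized.

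- All randomized: 1/7 = 14.3%.
- By arm: the split is not given. Assuming all 7 were dosed, a 5:2 split gives 1/5 = 20% (CHF6563) or 1/2 = 50% (morphine), and a 4:3 split gives 1/4 = 25% or 1/3 = 33.3%.

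The table counts babies with at least one event. The overall treatment-emergent row therefore moves only if the affected baby has no other treatment-emergent event. Likewise, a serious, severe, death or discontinuation row moves only if that baby has no other event qualifying for that row. The row's event count falls by one in either case.

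**The case against.** **Protocol 10.8 may already cover this.** It can be read as making an important on-drug change an adverse event of its own, with a post-dose start, and such an event would be counted. That reading is fair. Equally, nothing states that a change must be written over the old record: Protocol 7.1.3 says only that changes are recorded, and that could mean resolution or outcome. But 10.8 does not say what to do when the event is already open, so sites could differ.

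**Few events may qualify.** Exclusion criterion 5 removes babies with medical illness at randomization. Signs of NOWS are not adverse events unless unusual or suggestive of another diagnosis. A new apnea or desaturation episode after dosing has its own start time. Where consent is given only once signs appear, the pre-dose window is short. All of this stands and limits how often the gap would matter.

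**A reader might infer that these events vanish from the report.** They do not. SAP 3.1.3 lists every adverse event, and Listing 16.2.7.1 gives all the information collected on pre-treatment events. Deaths also require a narrative (Protocol 10.11), and the ISMB reviews serious events (Protocol 10.12). What is lost is the count, and the place under the outcome heading where a reader would look.

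**A reader might also infer that the plan's adverse event counts are biased downwards overall.** That goes too far. This rule can only omit events, but the worst-case rules for incomplete start times and for peri-dosing events push the other way.

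**The trial stopped at 7 babies and no statistical analysis is planned.** This is true. It confines the effect to one overview table and a set of sub-listings.

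**Conclusion.** The point holds as a defect in a stated rule. Both documents define treatment-emergent status by start time with no worsening clause. Unless a site opens a new record, an event with a known pre-dose start that worsens, turns serious or fatal, or leads to drug withdrawal after the first dose is absent from Table 14.3.1.1 and from the treatment-emergent sub-listings. The SAP follows the protocol here, so this is a shared gap and not a contradiction between them.

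The size is one baby in 7 (14.3%) for each such case, subject to the condition on other events given above. The arm-level percentages rest on an assumed split. The documents do not show that any such event occurred, and they do not support quoting a fixed undercount in percentage points.

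**What to change.** In SAP 3.1.2, define a treatment-emergent event as one that starts on or after first study drug administration, or that starts before it and then, on or after first administration, increases in intensity, becomes serious or fatal, or leads to drug withdrawal. Make the pre-treatment class exclude such events, and let this flag override the start-based phase for the table and sub-listings. Record it in SAP section 6 as a change from Protocol 12.3.7.

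Fatal and drug-withdrawn cases can be derived from the outcome and action-taken fields already collected, because in a dosed baby both necessarily follow the first dose. Changes in intensity or seriousness need a data query, limited to pre-treatment events ongoing at first dose in the dosed babies. Asking sites to split old records retrospectively is unnecessary.

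The cost is a short SAP edit and a short query in at most 7 babies. Treatment-emergent counts may rise slightly.

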5.2 PHASES AND TIME POINTS

5.2.1 *Phases*

Adverse events, medications, and procedures will be allocated to phases. For assessments, the visit and time point labels indicated on the subject's case report form (CRF) will be used to allocate to the correct treatment.

Adverse events, procedures and medications:

Phase	Start	End
Screening	Date of signing the ICF, with 00:00 added as time part	First administration date(time) – 1 minute
Treatment	First administration date(time)	Last administration date(time) + 48 hours
Follow-up	End date(time) of treatment phase + 1 minute	Date of last contact, with 23:59 added as time part

Per definition, and for each subject, the first phase starts on the date of the earliest available ICF signature, with 00:00 added as time part. The last available phase ends on the date of last contact, with 23:59 added as time part.

All tables and listings will present treatments rather than phases.

AEs, medications and procedures will be allocated to phases as described in sections 3.1.2 and 4.5.2 respectively.

In addition to the analysis phases described above, a subject will be considered to have entered a specific study phase based on the below definitions:

- Initiation phase: all subjects in the safety set
- Escalation phase: all subjects receiving at least one dose higher than the initial dose
- Stabilization phase: all subjects who receive at least 2 consecutive doses without escalation
Note: Subjects can skip the escalation phase and directly enter the stabilization phase from the initiation phase.
- Weaning phase: all subjects who receive at least one dose lower than the previous
- Cessation phase: all subjects reaching the cessation dose (i.e. between 90-110% of the initial dose for CHF6563 or < 0.025 mg/kg for morphine) and having a decrease in dose frequency (only subjects receiving CHF6563, i.e. dosing frequency is decreased q24 hours)

Note: in addition to the above definitions, other information present in SDTM (i.e. flags or visits present indicating that a subject has entered a specific phase) could be used to determine whether a subject entered a specific phase. A phase (and all subsequent phases previously entered by the subject) will be considered discontinued whenever a subject discontinues the study during that study phase.

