5.3 IMPUTATION AND ROUNDING RULES

5.3.1 *Missing values*

Potential imputations of missing values will be discussed during the review of the data by the Chiesi team. Decisions on whether any imputation rules on missing values should be applied to the analysis will be fully documented in the DRR.

5.3.2 *Values below or above a threshold*

Safety values expressed as below (or above) the limit of quantification will be imputed by the value of the quantification limit itself.

PK concentrations below the quantification limit will be flagged as BLQ in the concentration listing. Listings will always show the non-imputed values.

5.3.3 *Rounding of derived variables*

[figure not shown]
Derived variables will be rounded to the appropriate number of decimals at TLF level:

- Duration of treatment/adjunctive therapy (hours) will be presented with 1 decimal.
- Time to weaning (hours) will be presented with 1 decimal.
- Percentage of total amount of active study drug which is from rescue doses will be presented with 1 decimal.
- Percentiles will be presented with 1 decimal.
- Mean blood pressure will be presented with 1 decimal.
- PK concentrations will be presented with 3 significant digits except values >1000, which will be presented without decimals.
- AE duration will be presented with 1 decimal.

Rounding will be done using the round half away from zero tie-breaking rule (see Definition of terms).

5.3.4 *Outliers*

No data will be excluded from the analysis.

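### SAP 3.1.2 adds a whole hour to any adverse event duration shown in hours, so a 60-minute event is listed as 2.0 h; the error is confined to the AE listings

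*SAP*

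**What the plan says.** SAP section 3.1.2 gives parallel formulas for AE duration, one per display unit:

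- "In minutes: AE end date/time – AE start date/time + 1 minute"
- For hours, the end date/time minus "AE start date/time + 1 hour"
- For days, it subtracts dates and adds one day.

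These apply under the condition "AE onset and duration will be calculated as follows when start and stop dates are fully known".

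A note in the same section chooses the unit. For the shortest events, "If AE duration is less than 1 hour, the duration will be presented in minutes". For the next band, "If the AE duration is 1 hour or more, but less than 1 day, it will be presented in hours". Longer events are shown in days. The note does not say whether plain elapsed time or a derived duration is compared with the cut-offs.

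Section 5.3.3 adds: "AE duration will be presented with 1 decimal".

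On time resolution, section 3.1.2 says that start and stop dates are collected with a time part given in parentheses. The analysis-phase table in section 5.2.1 works to the minute; for example, follow-up begins at "End date(time) of treatment phase + 1 minute". Section 3.1.2 also ends the pre-treatment period one minute before first dosing.

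Duration is named as a column in listings 16.2.7.1, 16.2.7.2 and 16.2.7.10. Listings 16.2.7.3 to 16.2.7.9 are defined as subsets of 16.2.7.2 and inherit it.

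**The concern.** Adding one unit makes a duration inclusive of its end point, and the unit added has to match the resolution at which the end points were recorded. One day is right for dates, and one minute is right for times held to the minute. The hours line uses the same two date/time variables as the minutes line but adds sixty times as much. It looks as if the pattern of adding one of whatever unit is displayed was carried over without checking the resolution.

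The SAP's other durations in hours do not follow this pattern. Duration of treatment (2.1.1) and time to first weaning (2.2.2) are plain differences with nothing added.

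At stake is the accuracy of one derived column in the AE listings. SAP v2.0 drops most derivations but keeps this one. With seven randomized neonates the safety data will be read row by row, so a wrong value in a row is what the reader sees.

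**Working it through.** **Inputs.** The two formulas and the unit cut-offs come from SAP 3.1.2, and the one-decimal display with halves rounded away from zero comes from SAP 5.3.3. The documents contain no worked AE duration, so there is no stated figure to reproduce. The elapsed times below are illustrations.

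**Formulas**, with m = elapsed minutes (end minus start):

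- Minutes rule as written: m + 1 minutes
- Hours rule as written: m/60 + 1 hours
- Hours with the minutes rule's convention: (m + 1)/60 hours

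| m (min) | As written, m/60 + 1 | Elapsed hours, m/60 | (m + 1)/60, one decimal | Excess of the written rule over elapsed |
|---|---|---|---|---|
| 60 | 2.0 | 1.0 | 61/60 = 1.0 | 100% |
| 90 | 2.5 | 1.5 | 91/60 = 1.5 | 67% |
| 120 | 3.0 | 2.0 | 121/60 = 2.0 | 50% |
| 240 | 5.0 | 4.0 | 241/60 = 4.0 | 25% |
| 720 | 13.0 | 12.0 | 721/60 = 12.0 | 8.3% |

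The excess over elapsed time is always exactly 1 hour. Against the one-minute convention it is 59 minutes.

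**Does another reading rescue the 60-minute case?**

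- Count the 60 minutes inclusively, so that 59 have elapsed: 59/60 + 1 = 1.98, shown as 2.0.
- Truncate both clock times to the hour first: an event from 10:20 to 11:20 gives 11 − 10 + 1 = 2. The result is 2 for every start minute. The SAP does not mention truncation, and a one-decimal display would serve no purpose if it were intended.

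**At the cut-offs**, the result depends on what selects the unit:

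- *Elapsed time selects.* 59 minutes goes to the minutes rule and lists as 59 + 1 = 60 minutes, while one minute more lists as 2.0 h. An event of 23 h 59 min (m = 1439) stays in hours and lists as 1439/60 + 1 = 24.98, shown as 25.0 h, in a band meant for events shorter than a day.
- *The minutes-rule value selects.* 59 minutes becomes 60, counts as an hour, and lists as 59/60 + 1 = 1.98, shown as 2.0 h. 23 h 59 min becomes 1440 minutes and moves to days. 23 h 58 min stays in hours and lists as 1438/60 + 1 = 24.97, shown as 25.0 h.
- *The hours-rule value selects.* Nothing can fall below 1 hour, because m = 0 already gives 1.0, so the minutes rule is never used. A 23-hour event reaches 1380/60 + 1 = 24.0 and moves to days.

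The 60, 90 and 120-minute results are the same under all three.

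**The case against.** The strongest reply is that this hardly matters, and most of that reply stands. Duration feeds no table: the only AE table, 14.3.1.1, counts subjects and events. Allocation to phase and to the peri-dosing window uses the AE start time, so no event changes category. The listings are to carry all collected information for an AE on one line, so start and stop should sit beside the derived value, where a reader can see the discrepancy. SAP section 6.1 already says that the objectives cannot be evaluated with seven subjects and that no statistical analysis will be done. All of this limits the consequence. None of it makes the formula right.

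It is also fair to object that recording to the minute is inferred. The SAP leaves the time part of AE dates optional, and the case report form is not among the documents. The one-minute offsets in 3.1.2 and 5.2.1 make the inference reasonable. Truncation to the hour would still give 2 hours for a 60-minute event.

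A reader might infer that brief apneas, desaturations or bradycardias are the events most distorted. The documents do not support that. They give no durations for such events. The 10-minute peri-dosing window concerns when an event occurs relative to dosing, not how long it lasts. Unless the hours rule's own output selects the unit, which would leave the minutes rule unused, an event well under an hour goes to the minutes rule and never meets the extra hour.

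**Conclusion.** The hours formula is wrong as written, and no other part of the SAP corrects it. It overstates by about one hour each AE shown in hours with complete start and stop times. The relative error is 100% at 60 minutes and falls to 8.3% at 12 hours. These figures assume that the formula is applied literally to times held to the minute. The results at 59 minutes and at 23 h 59 min further assume that elapsed time selects the unit, and should not be quoted without that condition.

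Severity is minor. The error is confined to the duration column of listings 16.2.7.1 to 16.2.7.10. It would be too strong to infer that the safety summary is distorted: no AE count, table, phase allocation or conclusion depends on this value. The documents do not show whether any of the seven neonates had an AE in the affected range.

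**What to change.** Replace the hours line in SAP 3.1.2 with (AE end date/time − AE start date/time + 1 minute), computed in minutes, divided by 60 and shown to one decimal. State that the 1-hour and 1-day cut-offs are applied to this same value before rounding.

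An elapsed 58 minutes then lists as 59 minutes. An elapsed 59 minutes gives 60/60 = 1.0 h, and 60 minutes gives 61/60, also shown as 1.0 h, so the jump disappears. An event of 23 h 59 min gives 1440/60 = 24.0 h, meets the 1-day cut-off and passes to the days rule, which needs no change here.

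The cost is one line in the SAP and one in the program, plus a rerun of the AE listings if they have already been produced. No other output changes.
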